4.2.3 End of Treatment

An EoT visit should occur 28 (± 7) days from the last dose of the study treatment, and in any case prior to the initiation of new anticancer treatment.

When EoT visit coincides with a scheduled visit, the scheduled visit will become EoT visit.

4.2.4 Follow-up Period

All patients, regardless of disease status, will be followed for up to 5 years from EoT, or until withdrawal of consent, loss to follow-up, or death, whichever occurs first. All patients will be followed every 12 weeks for 1 year, then every 24 weeks for up to 3 years then annually for up to 5 years from EoT.

When disease assessments are not planned for a follow-up visit, respective visit can be done by phone.

4.2.5 End of Study

The end of study (EoS) occurs at the last scheduled visit/procedure for the last patient, unless the study is terminated earlier by Sponsor. The date of death of individual patient is considered as EoS whose survival status was informed at any later contact date.

4.3 Steering Committee (SC)

A Steering Committee (SC) has been established for the study. It is composed of global DLBCL experts, who may participate in the study, and the Sponsor's representatives. The SC will collaborate with the Sponsor throughout the conduct of the trial by providing insights and recommendations towards successful study execution, assist with data interpretation, and advise if changes to the trial are warranted. More details can be found in the Steering Committee charter.

5 Patient Population

Patients must meet all inclusion criteria and none of the exclusion criteria to be eligible for the study. All criteria have to be assessed during screening, unless otherwise specified.

Prospective approval of protocol deviations to recruitment and enrollment criteria, also known as protocol waivers or exemptions, is not permitted.

5.1 Inclusion Criteria

Inclusion Criteria for both cohorts:

1. Male or female
2. Pathologic diagnosis of DLBCL, as defined by the 2016 World Health Organization (WHO) classification (including patients with DLBCL transformed from indolent lymphoma), or high-grade B cell lymphoma (HGBCL), or Grade 3b follicular lymphoma (FL).
3. Measurable disease as defined by the 2014 Lugano Classification ([Appendix 12.2](#)).
4. Stages I-IV
5. Eastern Cooperative Oncology Group scale of performance status (ECOG PS) 0-2; ECOG PS 3 allowed if decline in status is deemed related to lymphoma & felt to be potentially reversible by the treating physician
6. Adequate organ function as defined by screening laboratory values within the following parameters:
 - a. Absolute neutrophil count (ANC) $\geq 1.0 \times 10^3/\mu\text{L}$ (off growth factors at least 72 hours)
 - b. Platelet count $\geq 75 \times 10^3/\mu\text{L}$ without transfusion in the past 7 days
 - c. Alanine aminotransferase (ALT), AST, and GGT $\leq 2.5 \times$ the upper limit of normal (ULN)
 - d. Total bilirubin $\leq 1.5 \times$ ULN (patients with known Gilbert's syndrome may have a total bilirubin up to $\leq 3 \times$ ULN)
 - e. Calculated creatinine clearance $> 30 \text{ mL/min}$ by the Cockcroft and Gault equation
- Note: A laboratory assessment may be repeated a maximum of two times during the screening period to confirm eligibility.
7. Women of childbearing potential (WOCBP)* must agree to use a highly effective** method of contraception from the time of giving informed consent until at least 12 months after the last dose of study treatment. Men with female partners who are of childbearing potential must agree to use a condom when sexually active or practice total abstinence from the time of the first dose until at least 7 months after the patient receives her/his last dose of study treatment

* WOCBP are defined as sexually mature women who have not undergone bilateral tubal ligation, bilateral oophorectomy, or hysterectomy; or who have not been postmenopausal (i.e., who have not menstruated at all) for at least one year. A postmenopausal state is defined as no menses for 12 months without an alternative medical cause. A high follicle stimulating hormone (FSH) level in the postmenopausal range may be used to confirm a postmenopausal state in women not using hormonal contraception or hormonal replacement therapy. However, in the absence of 12 months of amenorrhea, a single FSH measurement is insufficient.

** Highly effective forms of birth control are methods that achieve a failure rate of less than 1% per year when used consistently and correctly. Highly effective forms of birth control include: hormonal contraceptives associated with inhibition of ovulation (oral, injectable, patch, and intrauterine devices), male partner sterilization, or total abstinence from heterosexual intercourse, when this is the preferred and usual lifestyle of the patient.

Note: The double-barrier method (e.g., synthetic condoms, diaphragm, or cervical cap with spermicidal foam, cream, or gel), periodic abstinence (such as calendar, symptothermal, post ovulation), withdrawal (coitus interruptus), lactational amenorrhea method, and spermicide-only are not acceptable as highly effective methods of contraception.

Inclusion Criteria specific for Cohort A:

8. Unfit as defined by the sGA (includes all of the following):
 - a. Aged \geq 80 years
 - b. ADL score of 6
 - c. IADL score of 8
 - d. CIRS-G: no score of 3-4 and $<$ 5 scores of 2

Inclusion Criteria specific for Cohort B:

9. Frail as defined by the sGA:
 - a. Aged \geq 80 years
 - b. ADL score of $<$ 6 and/or
 - c. IADL score of $<$ 8 and/or
 - d. CIRS-G: \geq 1 score of 3-4 and/or \geq 5 scores of 2

OR

10. Aged \geq 65 - $<$ 80 with at least one of the following cardiac comorbidities that make anthracycline-containing regimens inadvisable as determined by the investigator
 - a. Left ventricular ejection fraction (LVEF) \geq 30 to $<$ 50%
 - b. History of myocardial infarction within 6 months prior to screening
 - c. Ischemic heart disease

d. History of stroke within 12 months prior to screening

5.2 Exclusion Criteria

1. Known history of hypersensitivity to or positive serum human anti-drug antibody to a CD19 antibody
2. Previous therapy for DLBCL, HGBCL, or Grade 3b FL (with exception of corticosteroid course for symptom management of less than 14 days)
3. Previous therapy with loncastuximab tesirine and rituximab for any indication
4. Known history of hypersensitivity to any component of study treatment (loncastuximab tesirine and rituximab)
5. Human immunodeficiency virus (HIV) seropositive with any of the following:
 - a. CD4+ T-cell (CD4+) counts < 350 cells/ μ L
 - b. Acquired immunodeficiency syndrome (AIDS) – defining opportunistic infection within 12 months prior to screening
 - c. Not on anti-retroviral therapy, or on anti-retroviral therapy for < 4 weeks at the time of screening
 - d. HIV viral load \geq 400 copies/mL
6. Serologic evidence of chronic hepatitis B virus (HBV) infection and unable or unwilling to receive standard prophylactic antiviral therapy or with detectable HBV viral load
7. Serologic evidence of hepatitis C virus (HCV) infection without completion of curative treatment or with detectable HCV viral load
8. History of Stevens-Johnson syndrome or toxic epidermal necrolysis
9. Lymphoma with active central nervous system involvement at the time of screening, including leptomeningeal disease
10. Clinically significant third space fluid accumulation (i.e., ascites requiring drainage or pleural effusion that is either requiring drainage or associated with shortness of breath)
11. Major surgery, radiotherapy, chemotherapy, or other anti-neoplastic therapy within 14 days prior to start of study drug (Cycle 1 Day 1 [C1D1]), except shorter if approved by the Sponsor
12. Use of any other experimental medication within 14 days prior to start of study drug (C1D1)
13. Received live vaccine within 4 weeks of C1D1
14. Congenital long QT syndrome or a corrected QTcF interval of > 480 ms at screening (unless secondary to pacemaker or bundle branch block)
15. Active second primary malignancy other than non-melanoma skin cancers, non-metastatic prostate cancer, in situ cervical cancer, ductal or lobular carcinoma in situ of the breast, or other malignancy that the Sponsor's Medical monitor and Investigator agree, and document should not be exclusionary

16. Any other significant medical illness, abnormality, or condition that would, in the Investigator's judgment, make the patient inappropriate for study participation or put the patient at risk

5.3 Screening Failures

Patients who signed the ICF but were found not eligible for the study prior to receiving study drug are defined as screening failures.

For these patients, only limited information will be collected in the electronic case report form (eCRF):

- Informed consent
- Demographics
- Inclusion/exclusion criteria
- Serious adverse event (SAE) and/or death occurring during the Screening Period
- Screen Fail (documenting primary reason for screen failure)

5.4 Re-screening Procedures

A patient who did not meet the eligibility criteria, i.e., screening failure, may be considered for re-screening. Decision for re-screening must be confirmed by the Sponsor/Medical monitor. A re-screened patient will be assigned a new patient number. Patients who are rescreened are required to sign a new ICF.

5.5 Discontinuation

The reason for discontinuation, whether it is from study treatment or from study, and the date of discontinuation will be recorded for all patients in the eCRF.

Note: Once discontinued from the study for any reason, patients will not be permitted to be re-enrolled.

5.5.1 Discontinuation from Study Treatment

A patient may be discontinued from the study treatment for any of the following reasons:

- Adverse event
- Patient decision
- Investigator decision
- Major protocol deviation
- Lost to follow-up
- Disease progression (radiographic or clinical)
- Study termination by the Sponsor

- For Cohort A, patients who did not achieve a CR or PR after 3 cycles
- For Cohort B, patients who do not achieve a CR or PR or SD after 3 cycles
- Other

A patient with any of the following reasons will be immediately discontinued from study treatment:

- Pregnancy
- Death

IMPORTANT: Study treatment discontinuation is not equivalent to discontinuation from the study. Patients discontinuing the study treatment will be asked to perform an EoT visit ([Section 4.2.3](#)) and continue with the Follow-up period ([Section 4.2.4](#)) as per protocol.

The investigational site should make every effort to complete follow-up per protocol. If patients are unable to return to the site, patient status, including but not limited to survival status, may be obtained by site staff via phone, email, or mail.

5.5.2 Discontinuation from the Study

A patient may be discontinued from the study for any of the following reasons:

- Study completion
- Withdrawal of consent
- Investigator decision
- Lost to follow-up
- Study termination by the Sponsor
- Death
- Other

If a patient withdraws informed consent for study participation, no additional study data will be collected.

The Sponsor may continue to use previously collected medical research data prior to the withdrawal consistent with the original authorization. If a patient withdraws from the study, he/she may request destruction of any samples taken and not tested, and the investigator must document this in the site study records.

The study may be terminated at any time, for any reason, by the Sponsor. Patients still receiving study drug will have an EoT visit as described in [Section 4.2.3](#) and schedule of events (SoE) ([Table 2](#)).

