15. Active second primary malignancy other than non-melanoma skin cancers, non-metastatic prostate cancer, in situ cervical cancer, ductal or lobular carcinoma in situ of the breast, or other malignancy that the Sponsor's Medical monitor and Investigator agree, and document should not be exclusionary
16. Any other significant medical illness, abnormality, or condition that would, in the Investigator's judgment, make the patient inappropriate for study participation or put the patient at risk

Estimated Duration of Patient Participation and Study Duration:

The duration of the study participation for each patient is defined as the time from the date of signed written informed consent to the completion of the follow-up period, withdrawal of consent, loss to follow-up, or death, whichever occurs first.

The study will include a Screening Period (up to 28 days), a Treatment Period (4-6 cycles [each of 3 weeks]), and a Follow-up Period (up to 5 years after treatment discontinuation).

After the last dose of Lonca-R, all patients will be followed every 12 weeks for 1 year, then every 24 weeks for up to 3 years, then annually up to 5 years.

The visits will be generally completed at the clinic. However, when disease assessments are not planned for a follow-up visit, the visit can be done by phone.

Patients who have progressed will be followed for survival for up to 5 years after the last dose of study drug.

The end of study occurs at the last scheduled visit/procedure for the last patient, unless the study is terminated earlier by the Sponsor.

Efficacy Assessments:

Disease assessments: positron emission tomography-computed tomography (PET-CT) Note: If the disease is not fluorodeoxyglucose (FDG)- avid at baseline, CT or magnetic resonance imaging (MRI) may be used. The assessment method determined to identify sites of disease at baseline should be used for all subsequent assessments.

Safety Assessments:

- Physical examination
- ECOG PS
- Height and weight
- Vital signs
- Pregnancy test, if applicable
- Safety laboratories (hematology, chemistry, urinalysis)
- AEs/SAEs, grading per Common Terminology Criteria for Adverse Events (CTCAE), version 5.0
- Patient-reported outcomes (PROs)
- Blood sampling for PK, ADA **CCI** [REDACTED]
- **CCI** [REDACTED]

Other Assessments:

Study Drug, Dosage, and Mode of Administration:

A treatment cycle is defined as every 3 weeks (Q3W)

- Lonca-R

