8.2 Eliciting and Reporting Adverse Events/Serious Adverse Events

Patients will be instructed to contact the Investigator at any time after ICF signature if any symptoms develop. At each study visit, patients will be asked a nonleading question to elicit any medically related changes in their well-being. Patients may also report AEs voluntarily and they will be instructed to contact the Investigator between visits if any symptoms develop or worsen.

AEs will be reported starting when the patient provides written informed consent. Clinically significant medical conditions present at the time of ICF signature will be reported as medical history. Clinically significant medical conditions that start or worsen after ICF signature will be reported as AEs.

All AE/SAEs regardless of relationship to study drug, will be reported from the time the patient signs the ICF until 15 weeks after the last dose of study drug or the start of new anti-cancer therapy, whichever is earlier; thereafter only related SAEs will be reported.

Whenever possible, AEs should be reported as a diagnosis rather than individual signs and symptoms. If no diagnosis is available or has been identified, then the primary symptom is reported.

In general, the term ‘disease progression’ should not be used for reporting an AE/SAE. However, AEs/SAEs that are complications of disease progression should be reported.

All AEs reported or observed during the study will be recorded on the AE page of the eCRF. Information to be collected will include event term, date of onset, assessment of severity ([Section 8.3](#)), seriousness ([Section 8.1](#)), relationship to study drug ([Section 8.4](#)), action taken with study drug, date of resolution of the event or ongoing (when no resolution by the end of the reporting period), any required treatment or evaluations, and outcome.

New SAEs and any recurrent episodes, progression, or complications of the original SAE must be reported to the drug safety department of the Sponsor or delegate (e.g., contract research organization [CRO]) within 24 hours after the time site personnel first learn about the event. Reporting will occur through the EDC system.

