2.2 Secondary Objectives

Cohort A and Cohort B

- Further evaluate the efficacy of Lonca-R
- To characterize the safety profile of Lonca-R
- To characterize the PK profile of Lonca when given in combination with rituximab
- To evaluate the immunogenicity of Lonca when given in combination with rituximab
- To evaluate the impact of Lonca-R treatment on treatment-related and disease-related symptoms, patient-reported functions, and overall health status

Due to early termination of the study, patients are not followed up for sufficient time. Some endpoints for secondary objectives, such as progression-free survival (PFS), overall survival (OS) and patient reported outcome (PRO), will not be analyzed because of lack of sufficient follow up.

[figure not shown]
3 Study Design

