4.9.1 Adverse Events, Serious Adverse Events, and Deaths

4.9.1.1 Analyses of Adverse Events

An AE is defined as any untoward medical occurrence in a patient or clinical investigation subject administered a pharmaceutical product, which does not necessarily have to have a causal relationship with this study treatment.

A treatment-emergent AE (TEAE) is defined as an AE that occurs or worsens in the period extending from the first dose of study drug to 15 weeks after the last dose of study drugs in this study (either loncastuximab or Rituximab) or start of a new anticancer therapy, whichever is earlier. The primary focus of adverse event reporting will be on TEAEs.

AEs will be coded according to MedDRA Version 24.1, and the severity of the toxicities will be graded according to the National Cancer Institute (NCI) Common Terminology Criteria for Adverse Events (CTCAE) Version 5.0, where applicable.

The summary of overall TEAEs includes:

- TEAEs
- Drug-related TEAEs (loncastuximab tesirine or Rituximab)
- Grade ≥ 3 TEAEs
- Drug-related Grade ≥ 3 TEAEs (loncastuximab tesirine or Rituximab)
- Serious Adverse Events (SAEs)

- TEAEs leading to dose delayed, reduced or interrupted (loncastuximab tesirine or Rituximab)
- TEAEs leading to discontinuation of loncastuximab tesirine or Rituximab
- TEAEs leading to death
- Infusion related reaction

The incidence of TEAEs will be summarized by system organ class (SOC) and preferred term (PT). A patient will be counted only once within a SOC and PT, even if the patient experienced more than one AE within a specific SOC and PT.

- All TEAEs \geq Grade 3 by PT, showing number (%) of patients with at least one TEAE, sorted by decreasing incidence of PTs
- All TEAEs by primary System Organ Class (SOC) and PT, showing number (%) of patients with at least one TEAE, sorted by SOC in alphabetic agreed order and decreasing incidence of PTs within SOC. This sorting order will be applied to all other tables, unless otherwise specified.
- All TEAEs by primary SOC, PT and Maximal CTCAE grade, showing number (%) of patients with at least one TEAE, sorted by SOC and PT in alphabetic order. This sorting order will be applied to all other tables, unless otherwise specified.
- All TEAEs \geq Grade 3 by primary SOC, PT and Maximal CTCAE grade
- All related TEAEs by primary SOC, PT and Maximal CTCAE grade (including possibly related, probably related, or related)

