4.9.1.2 Deaths

The following deaths summaries will be generated on the all-treated population.

- Number (%) of patients who died during the study and reasons for death
- Number (%) of patients who died within 15 weeks after the last dose of study drug (excluding those who died after taking any subsequent anticancer therapy/procedure) and reasons for death

Listing of deaths will be provided.

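### The SAP's 15-week death percentage takes no account of follow-up time in a study that was stopped early, so any patient whose contact ended before day 105 without a recorded death counts as alive

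*Protocol*

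**What the plan says.** **The window.** Protocol 8.2 requires all AEs and SAEs to be reported "until 15 weeks after the last dose of study drug or the start of new anti-cancer therapy, whichever is earlier". The SAP's definition of a treatment-emergent event (4.9.1.1) covers the period "extending from the first dose of study drug to 15 weeks after the last dose of study drugs in this study", again cut short by new anticancer therapy.

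**The death summary.** SAP 4.9.1.2 lists "Number (%) of patients who died within 15 weeks after the last dose of study drug", leaving out deaths that follow any later anticancer therapy or procedure. It is run on the all-treated population, and SAP Section 4 makes the size of the analysis population the denominator of every percentage. Neither section mentions minimum follow-up, censoring or the number of patients followed to week 15.

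**Early termination.** SAP Section 1 dates the decision to stop the study at 20 Jul 2023, and SAP 3.2 puts the number treated by then at 41. SAP 2.2 states: "Due to early termination of the study, patients are not followed up for sufficient time". On that ground it drops PFS, OS and PRO. SAP 4.8.3 keeps duration of response, with censoring at the last valid tumor assessment.

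**Contact after treatment.** The EoT visit is 28 (±7) days after the last dose. Protocol 5.5.2 lists sponsor termination among the reasons for leaving the study and says: "Patients still receiving study drug will have an EoT visit as described in" Section 4.2.3 and the schedule of events. Protocol 5.5.1 lists sponsor termination among the reasons for stopping treatment and sends patients who stop into the EoT visit and then follow-up.

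**The follow-up anchor.** The synopsis says "After the last dose of Lonca-R, all patients will be followed every 12 weeks for 1 year". Section 4.2.4 says "All patients will be followed every 12 weeks for 1 year", within a schedule whose end it counts from EoT. The schedule of events also counts the follow-up period from EoT.

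**The concern.** A percentage of deaths within 15 weeks, taken over all treated patients, reads as a 15-week mortality figure. It is one only if every patient was observed to death, to new anticancer therapy or to day 105. Where contact ended sooner and no death was recorded, the patient stays in the denominator and adds nothing to the numerator, and the unobserved days are treated as survived.

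In a study that runs to plan this would rarely matter, because follow-up extends to 5 years. Here the sponsor stopped the study, and the SAP was written afterwards with shortened follow-up in view. It adapts the time-to-event endpoints to that fact but not the 15-week death figure. SAP Section 1 gives benefit-risk as the reason for stopping, so readers will look closely at deaths after treatment, and an undercount would favor the regimen.

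**Working it through.** The plan states no figure for this point. Its only design calculation, the table of exact confidence intervals for the complete response rate with n = 40 (SAP 3.2), reproduces to one decimal in all twelve cells. It plays no part here.

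**Step 1: the calendar, in days after the last dose.** The window closes at 15 × 7 = day 105. Follow-up visits have a ±14-day window (visit windows under the schedule of events).

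| Contact | Nominal | Range |
|---|---|---|
| EoT | 28 | 21 to 35 |
| First follow-up counted from the last dose (synopsis) | 84 | 70 to 98 |
| First follow-up counted from EoT (4.2.4), with EoT at day 28 | 28 + 84 = 112 | 98 to 126 |
| The same, using both windows | 112 | 21 + 84 − 14 = 91 to 35 + 84 + 14 = 133 |

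On the synopsis reading the visit always falls inside the window and leaves a tail of 7 to 35 days. On the 4.2.4 reading it can fall on either side of day 105. In either case, a patient who stays in follow-up has vital status established at this visit or a later one, and any death can be dated.

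**Step 2: who can be miscounted.** Only patients whose contact ended before day 105 without a recorded death or new therapy. For one last seen at EoT, 105 − 28 = 77 days are unseen, 73% of the window (70 to 84 days, 67% to 80%, over the EoT range).

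**Step 3: bounds without assumptions about risk.** Let d be the recorded qualifying deaths and m the number of patients in Step 2. With full follow-up the count would lie between d and d + m, so the percentage would lie between d/41 and (d + m)/41. The SAP reports d/41, the lower end. Each such patient adds 1/41 = 2.4 percentage points to the range. The documents do not give m.

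**Step 4: illustration under assumptions.** Assume a true 15-week risk p, a constant hazard, and a share s of patients last seen at day 28. The risk seen by EoT is 1 − (1 − p)^(28/105), and

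crude percentage = (1 − s)·p + s·[1 − (1 − p)^(28/105)].

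For p = 10%, the risk seen by EoT is 1 − 0.9^0.267 = 2.8% (2.1% at day 21, 3.5% at day 35).

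| Assumed p | s = 10% | s = 25% | s = 50% |
|---|---|---|---|
| 5% | 4.6% | 4.1% | 3.2% |
| 10% | 9.3% | 8.2% | 6.4% |
| 20% | 18.6% | 16.4% | 12.9% |
| 30% | 27.9% | 24.8% | 19.5% |

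The crude figure is about 0.93, 0.82 and 0.64 times p for the three shares. As a head count with p = 10%, the shortfall is (10 − 2.8) × k/41 points for k patients last seen at EoT: 0.9 points for k = 5 and 1.8 points for k = 10.

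**Step 5: does termination end contact?** Section 5.5.1 points to continued follow-up and allows patient status to be obtained by phone, email or mail. Section 5.5.2 makes termination a reason to leave the study and names no contact after EoT. Its EoT sentence covers only patients still on drug, so it does not address those already off drug but less than 15 weeks from the last dose. Section 4.2.5 lets the sponsor end the study early. Section 8.2 sets the 15-week reporting duty with no exception for termination. These sections do not give one answer.

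**The case against.** The case against is substantial.

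- **Contact is scheduled.** A reader might infer that nobody is seen between week 4 and week 16. The documents do not support that. The synopsis places a visit at day 84, and the ±14-day window on the 4.2.4 visit already admits day 105.
- **Time between visits is not unobserved.** Under 8.2, patients are asked about changes at every visit and are told to report symptoms in between. A visit shortly after day 105 covers the window by recall and dates any death. This stands for every patient who remains in follow-up.
- **The protocol does not limit terminated patients to an EoT visit.** A reader might infer this from 5.5.2, but the section does not say so, and 5.5.1 and 8.2 point the other way. What stands is a conflict to be resolved.
- **No bias is shown.** The documents give no number on drug at termination, no last-contact dates and no cut-off. SAP 2.2 speaks of endpoints such as PFS and OS, which the protocol defines at 2 and 3 years; it does not say that follow-up fell short of 15 weeks. This stands.
- **The effect is small beside sampling error.** For p = 10%, the shortfall is 0.36 of a death for k = 5 and 0.72 for k = 10, while the exact 95% interval for 4 deaths in 41 runs from 2.7% to 23.1%. True, but a one-sided error is not covered by such an interval, and a reader cannot see it without a completeness count.
- **Other outputs exist.** All deaths on study are summarized and listed, and disposition is listed by patient. A careful reader might piece follow-up together from these. That lowers the stakes but does not replace a stated count.

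**Conclusion.** The point holds as a cheap improvement to the SAP, not as a demonstrated bias. The 15-week death percentage ignores follow-up time and reports no completeness, in a study known to have been cut short. Any patient whose contact ended before day 105 without a recorded death is counted as alive, so the figure can equal or fall below the full follow-up value but cannot exceed it.

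The size cannot be computed. It is zero if every patient reached death, new therapy or day 105. Otherwise it is at most 2.4 percentage points per incompletely followed patient, on the assumption that the final all-treated population is the 41 stated in SAP 3.2. The modeled figures also rest on an assumed risk, a constant hazard and last contact at EoT.

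Two protocol inconsistencies bear on it: whether contact continues after EoT on termination (5.5.1 against 5.5.2), and whether the first 12-week visit is counted from the last dose (synopsis) or from EoT (4.2.4).

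**What to change.** 1. **SAP 4.9.1.2.** Report how many treated patients were observed to death, new anticancer therapy or day 105. Beside the crude percentage, give a 15-week estimate from the last dose that uses follow-up time, censored at the date last known alive. Handle new anticancer therapy consistently with the existing exclusion. Treating it as a competing event is the like-for-like choice, because with complete follow-up that estimate equals the crude percentage. Censoring at new therapy is also possible, but it answers a different question and should be labeled as such.
2. **Protocol 5.5.1, 5.5.2 and 8.2.** Reconcile them on what contact follows sponsor termination. Where feasible before database lock, obtain AE/SAE and survival status by phone at about week 15 after the last dose for every patient still inside the window at termination, including those already off drug.
3. **Synopsis and Protocol 4.2.4.** State one anchor for the follow-up visits.

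**Cost.** One extra table row and one estimate in the SAP, wording changes in the protocol, and a few phone contacts. If database lock waits for the last patient's week-15 contact, the delay is up to about 105 − 28 = 77 days (11 weeks) after that patient's EoT visit. If that is not acceptable, item 1 alone needs no new data and makes the gap visible.
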